10.1.11 Publication and Data Sharing Policy

Agreements regarding publication and data sharing are found in the individual Clinical Trial Agreements between the Sponsor and each Investigator. At a minimum, the trial and its results will be posted on ClinicalTrials.Gov.

10.1.12 Conflict of Interest Policy

Under the applicable regulations the trial sponsor may be required to submit a list of clinical investigators who conducted covered clinical studies and certify and/or disclose certain financial arrangements as follows:

a. Certification that no financial arrangements with an investigator have been made where trial outcome could affect compensation; that the Investigator has

- no proprietary interest in the tested product; that the Investigator does not have a significant equity interest in the sponsor of the covered trial; and that the Investigator has not received significant payments of other sorts; and/or
- b. Disclosure of specified financial arrangements and any steps taken to minimize the potential for bias.

Disclosable Financial Arrangements:

- c. Compensation made to the Investigator in which the value of compensation could be affected by trial outcome.
- d. A proprietary interest in the tested product, including, but not limited to, a patent, trademark, copyright or licensing agreement.
- e. Any equity interest in the sponsor of a covered trial, i.e., any ownership interest, stock options, or other financial interest whose value cannot be readily determined through reference to public prices. This requirement applies to all covered studies, whether ongoing or completed;
- f. Any equity interest in a publicly held company that exceeds \$50,000 in value. The requirement applies to interests held during the time the clinical investigator is carrying out the trial and for 1 year following completion of the trial; and
- g. Significant payments of other sorts, which are payments that have a cumulative monetary value of \$25,000 or more made by the sponsor of a covered trial to the Investigator or the Investigators' institution to support activities of the Investigator exclusive of the costs of conducting the clinical trial or other clinical studies (e.g., a grant to fund ongoing research, compensation in the form of equipment or retainers for ongoing consultation or honoraria) during the time the clinical Investigator is carrying out the trial and for 1 year following completion of the trial.

10.2 Additional Considerations

Not Applicable.

10.3 List of Abbreviations

ABI Ankle to Brachial Index	
AE Adverse Event	
AM Amnion	
BP Blood Pressure	
cGMP current Good Manufacturing Practices	
 	
cGTP current Good Tissue Practices	
CLI Critical Limb Ischemia	
CONSORT Consolidated Standards of Reporting Trials	
CRF Case Report Form CTCAE Common Terminology Criteria for Adverse Events	
CWIS Cardiff Wound Impact Schedule DFU Diabetic foot ulcer	
DSMB Data and Safety Monitoring Board	
eCRF electronic Case Report Form	
EDC Electronic Data Capture	
FDA Food and Drug Administration	
GCP Good Clinical Practice	
HA Hyaluronic acid	
HbA1c glycated hemoglobin A1c	
HC Heavy chain	
HCT/P Human cell or tissue based product	
ICF Informed Consent Form	
IB Investigator's Brochure	
ICH International Conference on Harmonization	
IDSA Infectious Diseases Society of America	
IEC Independent Ethics Committee	
IRB Institutional Review Board	
ITT Intent to Treat	
LOCF Last Observation Carried Forward	
MedDRA Medical Dictionary for Regulatory Affairs	
MRI Magnetic Resonance Imaging	
mg Milligram	
mmHg Millimeters Mercury	
NIH National Institutes of Health	
OR Operating Room	
PP Per Protocol	
PTB Probe to bone	
PTX3 Pentraxin-3	
SAE Serious Adverse Event	
SC Standard Care	
SOA Schedule of Activities	
SSTI Skin and Soft Tissue Infection	
TcPO2 Transcutaneous Pressure of Oxygen	
TTI TissueTech Inc.	
TW Taiwan	
UC Umbilical Cord	
UDI Unique Device Identification	

10.4 Protocol Amendments

Protocol modifications, except those intended to reduce immediate risk to study subjects, may be made only by TissueTech Inc. A protocol change intended to eliminate an apparent immediate hazard to subjects may be implemented immediately, provided the IRB/IEC is notified within 5 days.

Any permanent change to the protocol must be handled as a protocol amendment. The written amendment must be submitted to the IRB/IEC and the Investigator must await approval before implementing the changes. TissueTech Inc. will submit protocol amendments to the appropriate regulatory authorities for approval.

If in the judgment of the IRB/IEC, the Investigator, and/or TissueTech Inc., the amendment to the protocol substantially changes the study design and/or increases the potential risk to the subject and/or has an impact on the subject's involvement as a study participant, the currently approved written informed consent form will require similar modification. In such cases, informed consent will be renewed for subjects enrolled in the study before continued participation.

Summary of Changes from Previous Version:

Version	Affected Section(s)	Summary of Revisions Made	Rationale
1.0	N/A	Original Issue	
1.1	§ 2.2	Updated reference to TTAX01-CR001	TTAX01-CR001 was not completed at the time of original issue, it was completed at the time of this amendment
	§ 8	Clarified procedures on first observation of closure, removed statements that no dose or frequency would be recorded for ConMed and other treatments	Previous wording implied that nothing needed to be done at the visit where closure was first seen; corrected an error regarding data collection
	§ 9.2	Removed reference to single trial, added accrual assumption	Following request by FDA

Page 82 of 100

§ 10.1.5	Corrected e-mail address	Corrects an error
§ various	Spelling and grammatical errors corrected, updated wording in Cardiff Wound Impact Schedule	Opportunistic

12 APPENDIX

12.1 Decision Flow Diagrams for Placement of TTAX01

Figure 12.1-1. Treatment if there is no SSTI observed

[figure not shown]
[figure not shown]

Figure 12.1-2. Treatment if SSTI is observed without recurrence of clinical suspicion of osteomyelitis

[figure not shown]
[figure not shown]
[figure not shown]

Figure 12.1-3. Treatment if SSTI is observed with clinical suspicion of osteomyelitis

12.2 PROMIS Lower Extremity Function questionnaire

The subject will be asked to "Please respond to each question or statement by marking one box per row."

	Without any difficulty	With a little difficulty	With some difficulty	With much difficulty	Unable to do
Are you able to get on and off the toilet?	5	□ 4	3	□ 2	1
Are you able to step up and down curbs?	□ 5	□ 4	□ 3	□ 2	□ 1
Are you able to get in and out of a car?	□ 5	□ 4	□ 3	□ 2	□ 1
Are you able to get out of bed into a chair?	□ 5	□ 4	□ 3	□ 2	□ 1
Are you able to push open a heavy door?	□ 5	□ 4	□ 3	□ 2	□ 1
Are you able to run errands and shop?	□ 5	□ 4	□ 3	2	□ 1
Are you able to get up off the floor from lying on your back without help?	□ 5	□ 4	□ 3	2	□ 1
Are you able to go for a walk of at least 15 minutes?	5	4	3	2	1
	No difficulty	A little difficulty	Some difficulty	A lot of difficulty	Can't do
How much DIFFICULTY do you currently have standing up from an armless straight chair (e.g., dining room chair)?	5	4	3	2	1
How much DIFFICULTY do you currently have sitting down on and standing up from a chair with arms?	5	4	3	2	1
How much DIFFICULTY do you currently have moving from sitting at the side of the bed to lying down on your back?	5	4	3	2	1
How much DIFFICULTY do you currently have standing up from a low, soft couch?	□ 5	□ 4	□ 3	□ 2	□ 1

Page 94 of 100

How much DIFFICULTY do you currently have going up and down a flight of stairs inside, using a handrail?	5	□ 4	3	2	1
How much DIFFICULTY do you currently have walking on uneven surfaces (e.g., grass, dirt road or sidewalk)?	5	4	3	2	1
How much DIFFICULTY do you currently have walking around one floor of your home?	5	□ 4	□ 3	2	1
How much DIFFICULTY do you currently have taking a 20-minute brisk walk, without stopping to rest?	5	4	3	2	1
How much DIFFICULTY do you currently have walking on a slippery surface, outdoors?	5	□ 4	□ 3	2	1
How much DIFFICULTY do you currently have climbing stairs step over step without a handrail? (alternating feet)?	5	□ 4	3	2	1
How much DIFFICULTY do you currently have walking in a dark room without falling?	□ 5	□ 4	□ 3	□ 2	1

12.3 Cardiff Wound Impact Schedule

The subject will be provided with,	and asked to complete the following:
------------------------------------	--------------------------------------

How ofter	n do you see your	family and friend	s?
Daily □	Once a week □	Once a month □	Less than once a month \Box
How stres	ssful has this expe	erience been for yo	ou during the past 7 days?
		N	Not at all/

	not an an/ not applicable	Slightly	Moderately	Quite a bit	Very
Difficulty getting out and about	5	□ 4	3	2	1
Relying more on others	□	□	□	□	□
	5	4	3	2	1
Your family/friends being overly protective	□ 5	□ 4	□ 3	□ 2	1
Unable to enjoy your usual social life (e.g. hobbies)	□ 5	□ 4	3	2	1
Limited contact with family/friends	□	□	□	□	□
	5	4	3	2	1
Not going out for fear of bumping your wound site	□	□	□	□	□
	5	4	3	2	1
Wanting to withdraw from people	□	□	□	□	□
	5	4	3	2	1

Have you experienced any of the following during the past 7 days?

	Not at all/ not applicable	Seldom	Sometimes	Frequently	Always
Difficulty getting out and about	□ 5	□ 4	□ 3	□ 2	□ 1
Relying more on others	□ 5	□ 4	□ 3	2	□ 1
Your family/friends being overly protective	5	□ 4	□ 3	2	1
Unable to enjoy your usual social life (e.g. hobbies)	5	4	3	2	1

Page	06	of 1	$\Omega\Omega$
Fage	ソロ	OII	1111

111111				1 484 7 0 01 1	
Limited contact with family/friends	□ 5	□ 4	□ 3	□ 2	□ 1
Not going out for fear of bumping your wound site	5	□ 4	□ 3	2	1
Wanting to withdraw from people	□ 5	□ 4	□ 3	□ 2	1

To what extent do you agree/disagree with the following statements?

	Strongly disagree	Disagree	Not Sure	Agree	Strongly Agree
I feel anxious about my wound(s)	5	□ 4	3	2	1
I feel frustrated with the time it is taking for the wound(s) to heal	5	□ 4	3	2	□ 1
I am confident that the wound(s) I have will heal	□	□	□	□	□
	5	4	3	2	1
I worry that I may get another wound in the future	□	□	□	□	□
	5	4	3	2	1
The appearance of the wound site is upsetting	□	□	□	□	□
	5	4	3	2	1
I worry about bumping the wound site	□	□	□	□	□
	5	4	3	2	1
I worry about the impact of the wound(s) on my family/friends	5	□ 4	□ 3	2	□ 1

Have you experienced any of the following during the past 7 days?

	Not at all/ not applicable	Seldom	Sometimes	Frequently	Always
Disturbed sleep	5	□ 4	3	□ 2	□ 1
Difficulty in bathing	5	4	3	2	1

Page 97 of 100

Immobility around the home	□	□	□	□	□
	5	4	3	2	1
Immobility outside the home	□	□	□	□	□
	5	4	3	2	1
Leakage from the wound(s)	□	□	□	□	□
	5	4	3	2	1
Pain from the wound site	□	□	□	□	□
	5	4	3	2	1
Discomfort from the bandaging / dressing	□	□	□	□	□
	5	4	3	2	1
Unpleasant odor or smell from the wound(s)	□	□	□	□	□
	5	4	3	2	1
Problems with everyday tasks (e.g. shopping)	□	□	□	□	□
	5	4	3	2	1
Difficulty in finding appropriate footwear	□	□	□	□	□
	5	4	3	2	1
Problems with the amount of time needed to care for the wound site	□ 5	□ 4	□ 3	□ 2	1
Financial difficulties as a result of the wound(s)	□	□	□	□	□
	5	4	3	2	1

How stressful has this experience been for you during the past 7 days?

	Not at all/ not applicable	Slightly	Moderately	Quite a bit	Very
Disturbed sleep	5	□ 4	3	2	1
Difficulty in bathing	□ 5	□ 4	□ 3	2	□ 1
Immobility around the home	□ 5	□ 4	3	2	□ 1
Immobility outside the home	□ 5	□ 4	□ 3	2	□ 1
Leakage from the wound(s)	□ 5	□ 4	□ 3	2	□ 1
Pain from the wound site	□ 5	□ 4	□ 3	□ 2	□ 1
Discomfort from the bandaging / dressing	□ 5	□ 4	3	2	1

Page 98 of 100

Unpleasant odor or smell from the wound(s)	□ 5	□ 4	□ 3	2	□ 1
Problems with everyday tasks (e.g. shopping)	□ 5	□ 4	□ 3	2	□ 1
Difficulty in finding appropriate footwear	□ 5	□ 4	□ 3	□ 2	□ 1
Problems with the amount of time needed to care for the wound site	5	□ 4	□ 3	□ 2	1
Financial difficulties as a result of the wound(s)	□ 5	□ 4	□ 3	□ 2	□ 1

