3 OBJECTIVES AND ENDPOINTS

OBJECTIVES	ENDPOINTS	JUSTIFICATION FOR ENDPOINTS			
Primary					
To determine whether treatment of high grade DFU with standard care plus TTAX01 results in a higher probability of achieving complete wound closure over 26 weeks, compared with standard care alone.	Time from baseline to initial observation of healing, over 26 weeks, where healing has been confirmed at two consecutive visits each two weeks apart.	The endpoint complies with FDA guidance. Dropouts should be minimal during the first 26 weeks, but may increase thereafter. Analysis will use a Cox proportional hazard model			
Secondary					
To compare differences between treatment groups in proportions of wounds healed through 50 weeks	Proportions of wounds healed by Week 50	This endpoint provides insight into longer term benefits of the intervention			
To compare long term durability of closure between treatment groups	Proportions of wounds that re-ulcerate by Week 50	May provide insight into the quality of healing			
To compare limb preservation between treatment groups	Proportions of minor (portions of the foot) and major (ankle, above or below the knee) amputations following the initial procedure by Week 50	Each amputation risks loss of mobility, with consequent increased mortality			
To compare patient reported mobility (lower extremity function) between groups.	Total score on PROMIS Health Organization Neuro- QoL "Lower Extremity Function" at Study End.	The tool is an NIH validated measure of patient reported outcomes			
Safety					
To examine Quality of Life endpoints related to therapeutic intervention	Total score of quality of life assessment determined by Cardiff Wound Impact Schedule (CWIS) at Study End				
Proportion of subjects experiencing adverse events, by group	Spontaneously reported and elicited adverse events, coded in MedDRA				

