For total score of CWIS and PROMIS Questionnaires, the null hypothesis is that a total score (or better quality-of-life) of this measure will not be statistically different between the two treatment arms of this study at the end of study. The alternative hypothesis is that a greater total score (or better quality-of-life) of one or both of these measures will be seen for the SC plus TTAX01 arm at the end of study, compared to the SC alone arm.

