9.4.4 Safety Analyses

Safety measures will be reported as summary statistics during treatment, with shift tables provided for laboratory measures taken at baseline and end of study. Adverse events will be coded using the version of MedDRA available at the start of the trial. Each AE will be counted once for each subject unless it resolves and recurs, in which case it may appear as multiple AEs. Severity, frequency, and relationship of AEs to study intervention will be presented by System Organ Class (SOC) and preferred term groupings.

Listings will be provided for discontinuations, deviations, compliance, AEs leading to discontinuation, and AEs related to the index ulcer. AE listings will include severity and relationship to test article, as well as actions taken.

Tables will be provided summarizing reasons for screen failure, reasons for premature discontinuation, protocol deviations, subject compliance, treatment emergent AEs (TEAEs), TEAEs of interest, TEAEs by severity, SAEs, and AEs leading to discontinuation as well as total score of Cardiff Wound Impact Schedule (CWIS).

Where applicable, analyses of safety measures will be conducted, respectively, for the 26-week treatment period of the safety population and for the long-term observation period of the LO population. Missing values in safety measures will remain as missing in analyses.

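### The printed CWIS codes score confidence in healing in the wrong direction for a total that Section 9.1 reads as higher is better, and the protocol nowhere reverses the item

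*Protocol*

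**What the plan says.** **The form (Section 12.3).** One block is headed "To what extent do you agree/disagree with the following statements". It has seven statements under a single set of codes, from "Strongly disagree" = 5 to "Strongly Agree" = 1. Six statements are negative: anxiety, frustration, three worries, and upset at the wound's appearance. The seventh is positive: "I am confident that the wound(s) I have will heal". It has the same 5-4-3-2-1 row.

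**The direction (Section 9.1).** The alternative hypothesis for CWIS and PROMIS is that "a greater total score (or better quality-of-life) of one or both of these measures will be seen" in the TTAX01 arm. A higher CWIS total is therefore the favourable result.

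**The use of the total.** Section 3 lists, under Safety, "Total score of quality of life assessment determined by Cardiff Wound Impact Schedule (CWIS) at Study End". Section 9.4.4 puts the CWIS total in a summary table with the other safety measures, and missing safety values stay missing. Section 9.4.3 specifies an ANCOVA for PROMIS and names no CWIS analysis. The lists of secondary endpoints in Sections 9.1 and 9.4.3 do not include CWIS.

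**The concern.** A total has a direction only if every item that feeds it points the same way. Here the protocol prints the codes and also states the direction, and for one item the two disagree. Anyone who adds the printed codes gives a fully confident subject 1 and a subject with no confidence 5, then reads the higher total as the better one.

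At stake is the reading of one named endpoint. Any between-arm difference in confidence would be subtracted from the more confident arm when it should be added. TTAX01 is open label (Section 6.3), so the scoring rule is best fixed before the data are analysed; a later change could look like a choice made with results in view.

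A smaller inconsistency sits beside this. Section 9.1 gives CWIS a superiority hypothesis within the secondary efficacy hypotheses, while Section 3 classes it as Safety and Section 9.4.4 only summarises it.

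**Working it through.** The protocol states no CWIS range, standard deviation or expected difference, so there is no figure of its own to reproduce. The check counts the items, fixes their direction and works out the scoring error.

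**1. Coded items (Section 12.3).** The five coded blocks hold 7 + 7 + 7 + 12 + 12 = 45 items. The opening question on how often the subject sees family and friends has boxes without numbers and is not counted. A sum of printed codes runs from 45 × 1 = 45 to 45 × 5 = 225, a width of 180.

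**2. Direction of each block.**

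| Block | Items | Response coded 5 | Is 5 the better answer? |
|---|---|---|---|
| Social life, stress | 7 | no stress, or not applicable | yes |
| Social life, experience | 7 | not experienced, or not applicable | yes |
| Agree/disagree, negative statements | 6 | strong disagreement | yes |
| Agree/disagree, confidence statement | 1 | strong disagreement | **no** |
| Physical and daily living, experience | 12 | not experienced, or not applicable | yes |
| Physical and daily living, stress | 12 | no stress, or not applicable | yes |

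So 44 items follow the direction in Section 9.1 and one runs against it. That item is 1/45 = 2.2% of the total range and 1/7 = 14.3% of its own block.

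**3. Best and worst states.**
- Best, printed codes: 44 × 5 + 1 = 221. With the item reversed: 225.
- Worst, printed codes: 44 × 1 + 5 = 49. With the item reversed: 45.

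**4. Error per subject.** Let x be the printed code. The reversed code is 6 − x, so the correction is (6 − x) − x = 6 − 2x.

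| Answer | x | 6 − x | Correction to total |
|---|---|---|---|
| Strongly agree | 1 | 5 | +4 |
| Agree | 2 | 4 | +2 |
| Not sure | 3 | 3 | 0 |
| Disagree | 4 | 2 | −2 |
| Strongly disagree | 5 | 1 | −4 |

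**5. Error between arms.** Let d be the difference in mean confidence between arms on the correctly oriented 1-to-5 scale. The printed codes contribute −d to the difference in totals; the correct codes contribute +d. The error is d − (−d) = 2d. The documents give no d, so these values are assumptions:

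| Assumed d | Error in difference of totals | Share of the 180-point range |
|---|---|---|
| 0.25 | 0.5 | 0.3% |
| 0.5 | 1.0 | 0.6% |
| 1 | 2.0 | 1.1% |

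**6. Search for a reversal.** Sections 3, 8.1.1, 8.1.8, 9.1, 9.4.3, 9.4.4 and 12.3 all mention or bear on CWIS. None reverses the item.

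**The case against.** The strongest reply is that a form is not a scoring rule. Section 8.1.1 calls the appendix questionnaires examples, Section 12.3 presents this one only as something the subject fills in, and no section gives a formula for the total. The opening question has no codes at all, so the printed numbers may be response codes for data entry. Section 9.4.1 leaves data conventions to the SAP, and reversing a positive item is a routine derivation step. **This stands in part.** It lowers the certainty that the reported total will be wrong. It does not remove the conflict between the printed codes and the direction in Section 9.1, so the point concerns something the protocol states and not a missing detail.

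The reply on size also stands. One item in 45 is affected. CWIS is a safety-listed measure in a summary table, and if confidence is higher with TTAX01 the error works against TTAX01.

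Three stronger readings are tempting, and the documents do not support them:
- **An 8-point distortion.** Between a fully confident and a fully unconfident subject the printed contrast is 1 − 5 = −4 and the correct one is 5 − 1 = +4, a gap of 8, or 8/180 = 4.4% of the range. That compares two extreme people. It is not an expected difference between arms.
- **The item is where a treatment benefit would most likely show.** The endpoint is taken at study end. A healed subject may have no index ulcer left to be confident about, and this block has no not-applicable option. The documents do not say how such subjects would answer, so the sign and size of d are unknown.
- **CWIS needs its own formal test.** That is a separate design choice. The safety listing and the omission from the secondary endpoint lists agree with each other; the sentence out of line is the hypothesis in Section 9.1.

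**Conclusion.** The printed codes and the stated direction of the CWIS total conflict for one item. A total formed from the codes as printed is wrong by 6 − 2x per subject, at most 4 points either way, and the between-arm difference is wrong by 2d, against the more confident arm. With d assumed between 0.25 and 1 that is 0.5 to 2 points on a 180-point range.

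This rests on two assumptions: that the total is a simple sum of the printed codes, and that nothing outside the protocol reverses the item. The first is the plain reading of a total score but is not spelled out; the second cannot be checked without the SAP or a scoring manual. The conflict in the protocol is certain; an error in the final results is only possible. The primary endpoint, the sample size and the PROMIS score are untouched. It is a small correction, worth making because it costs almost nothing and removes a false direction from a named endpoint.

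**What to change.** **Scoring.** Add one sentence to Section 12.3 or 9.4: the confidence-in-healing item is reverse-scored, as 6 minus the printed value, before any CWIS total is formed, at screening and at study end. If the SAP or a scoring manual already does this, a cross-reference is enough.

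**Consistency (minor).** Bring the CWIS superiority hypothesis in Section 9.1 into line with the Safety listing in Section 3 and the summary-only reporting in Section 9.4.4. Deleting CWIS from that hypothesis is the simplest way; no particular CWIS test needs to be prescribed.

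**Cost.** One sentence, one line of programming and one edit to Section 9.1. No new data are needed, and forms already completed remain usable because the recorded answers do not change.
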